**Table 3 Schedule of assessments during treatment phase in case of exacerbation**

Assessment/ Activity	Daily PE treatment phase	Post daily PE (including PE tapering)
Treatment with study drug	Once daily or twice daily (only if twice daily PE) a	once daily $\pm$ 2 hours
Concomitant medication recording other than PE-related treatment	all	weekly $\pm$ 2 days
PE details b	all	NA or all in case of tapering
Subject review/clinical assessment, including vital signs	daily	weekly $\pm$ 2 days
AE recording	daily (all)	weekly $\pm$ 2 days (all)
Glasgow Coma Score	weekly if abnormal at screening	weekly if abnormal at screening and if subject hospitalised
Neurocognitive battery	no	no
Modified ITP bleeding score	daily	weekly $\pm$ 2 days
Clinically relevant bleeding	daily	weekly $\pm$ 2 days
12-lead ECG	daily if abnormal at baseline. on day 1 and day 4, 4-6 h post-study drug	weekly $\pm$ 2 days
Blood chemistry (local lab)	daily pre-PE	weekly $\pm$ 2 days
Haematology (local lab)	daily pre-PE	weekly $\pm$ 2 days
Coagulation variables (local lab)	Mon, Wed, Fridays	weekly $\pm$ 2 days
Cardiac marker (TnT or TnI) (local lab)	daily pre-PE if value > ULN in baseline or at day 1	weekly $\pm$ 2 days if value > ULN in baseline or at day 1
BNP or NT proBNP (local lab)	Mon, Wed, Fridays pre-PE if value > ULN in baseline or at day 1	weekly $\pm$ 2 days if value > ULN in baseline or at day 1
Brain damage markers (NSE, S $\beta$ 100) (central lab)	Mon, Wed, Fridays pre-PE	weekly $\pm$ 2 days

Assessment/ Activity	Daily PE treatment phase	Post daily PE (including PE tapering)
PK (central lab)	No	2 samples weekly: 
 
• prior to study drug, but after PE (in case of tapering)
 
• 4-8 h post-study drug
 

RICO (central lab)	daily pre-PE	weekly $\pm$ 2 days (pre-PE in case of tapering)
vWF (central lab)	No	coupled to PK above
FVIII chromogene (central lab)	No	coupled to PK above
ADA (central lab)	No	weekly until the last day of study drug administration
ADAMTS13 and anti-ADAMTS13 antibody titre (central lab)	No	1 week and 3 weeks after the very last PE, including tapering e
Spent plasma retrieval	No	no
Recuperate nurse sheet and/or AE diary	NA	Post-hospital discharge: weekly $\pm$ 2 days d

a Once or twice daily as detailed in the Treatment and Dosing Regimen for study drug Section 7.2 of the protocol.

b Including concomitant medication related and simultaneous to PE procedure.

c As soon as level of consciousness and attentiveness of the subject permits and environmental factors are appropriate to support neurocognitive testing

d Post-discharge bleeding and any other AEs will be recorded daily by the medically trained person administering the study drug. The medically trained person will be instructed to contact the investigator in case of unexpected or clinically relevant findings

e The 1-week and 3-weeks after the last day of PE (including tapering) sampling may be done at the weekly visit, even if not exactly 1 or 3 weeks

Blood chemistry includes glucose, AST, ALT, LDH, CRP, creatinine, urea (BUN), uric acid, protein, albumin, haptoglobin, Na, K, Ca, Mg and Cl.

Haematology includes haemoglobin, haematocrit, MCV, MCH, MCHC, full blood count including RBC, WBC, differential, reticulocytes, optical platelet count and immature platelet fraction. Coagulation variables include fibrinogen, aPTT, PT, INR, vWF:Ag and FVIII (chromogene or alternative method).

**Appendix II – Protocol ALX-0681-2.1/10: Definition of ‘Major’ Protocol Deviations (PDs) for Data Analysis**

Major PD categories	Remarks	Source	How to assess?	DVTERM	DVDECOD
Inclusion criteria					

If one inclusion criterion or more are not met subject may not be randomised;
 
 
18 years of age or older
 
Men or women willing to accept an acceptable contraceptive regimen
 
Subjects with clinical diagnosis of TTP
 
Necessitating PE
 
Subject accessible to follow-up
 
Obtained, signed and dated informed consent
 
	
For #6: IC has to be signed and dated by subject or legal representative before inclusion in the study
	
██████████ ██████████ ██████████ ██████████
	
Review of listings or edit checks
	
Inclusion criterion 1-6 not met
	
Eligibility criteria not met

Exclusion criteria					

If one or more exclusion criteria are met subject may not be randomised;
 
 
Platelet count greater or equal to 100,000/<math>\mu</math>L
 
Severe active infection indicated by sepsis (requirement for pressors with or without positive blood cultures)
 
Clinical evidence of enteric infection with E. coli 0157 or related organism
 
Anti-phospholipid syndrome
 
Diagnosis of disseminated intravascular coagulation (DIC)
 
Pregnancy or breast-feeding
 
Haematopoietic stem cell or bone marrow transplantation-associated thrombotic microangiopathy
 
Known congenital TTP
 
Active bleeding or high risk of bleeding
 
	
Essential laboratory assessments to be done and recorded in the CRF:
 
 
Local lab platelet count at screening/baseline (missing platelet count is major PD)
 
–
 
–
 
At least 1 anti-PL ab test at screening/baseline (no anti-PL result (anticardiolipin test) is major PD)
 
–
 
Neg. pregnancy test (urine or serum) (major PD if positive; minor PD
 
	
██████████
	
Review of listings or edit checks
	
Exclusion criterion 1-18 not met
	
Eligibility criteria not met

Major PD categories	Remarks	Source	How to assess?	DVTERM	DVDECOD
10. Uncontrolled arterial hypertension 11. Known chronic treatment with anticoagulant treatment that cannot be stopped safely, including but not limited to: 
 
- vitamin K antagonists
 
- heparin or low molecular weight heparin (LMWH)
 
- non-acetyl salicylic acid non-steroidal anti-inflammatory molecules
 
 12. Severe or life threatening clinical condition other than TTP that would impair participation in the trial 13. Subjects with malignancies resulting in a life expectation of less than 3 months 14. Subjects with known or suspected bone marrow carcinosis 15. Subjects who cannot comply with study protocol requirements and procedures. 16. Known hypersensitivity to the active substance or to excipients of the study drug 17. Severe liver impairment, corresponding to grade 3 toxicity defined by the CTCAE scale. For the key liver parameters, this is defined as follows: 
 
- bilirubin > 3 x ULN (need to differentiate isolated increase in indirect bilirubin due to haemolysis, this is not an exclusion parameter, but disease related)
 
- alanine aminotransferase/aspartate aminotransferase (ALT/AST) > 5 x ULN
 
- alkaline phosphatase (AP) > 5 x ULN
 
- gamma glutamyl transpeptidase (GGT) > 5 x ULN
 
 18. Severe chronic renal impairment, as defined by GFR < 30 mL/min	if negative but result dated up to 72 hrs after randomisation) 7. – 8. – 9. – 10. – 11. – 12. – 13. – 14. – 15. – 16. – 17. Screening/baseline Lab tests minimally required (i.e. if any of bilirubin, ALT or AST are missing or above limits in exclusion criterium, this is a major PD): - bilirubin (direct) - ALT and AST (if AP and/or $\gamma$ GT are missing -> minor PD) 18. Serum creatinine (calculate GFR by	

 

			

Major PD categories	Remarks	Source	How to assess?	DVTERM	DVDECOD
	Cockcroft-Gault equation, if < 30 ml/min then major PD) [there is no box in the CRF to enter the calculated GFR value; GFR calculation according to Cockcroft-Gault formula requires serum creatinine, body weight, and age of subject as variables				
Clinically relevant bleeding (CRB)					
If study drug administration is not stopped when clinically relevant bleeding occurred	Monitoring check of CRF and Check in DB for start date CRB = stop date study drug (note that study drug is reported on daily basis, in fact the date should be missing in 'EX'). Also the bleeding is to be reported as AE with action taken regarding trial med = dose interrupted	██████████ ██████  ██████████ ██████	Review of listings or edit checks	Bleeding occurred but drug not interrupted	Investigator mistake
If study drug is restarted when vWF:Ag < 50% and FVIII not normalised	Monitoring check of CRF and Check in DB for start date of study drug ≥ date of local lab vWF:Ag > 50% and FVIII value in normal range	██████████ ██████  ██████████ ██████	Review of CTMS entries and listings Review of listings or edit checks	Drug restarted but vWF:Ag and FVIII levels not recovered yet	Investigator mistake
Study drug administration					
During daily PE treatment period					
Excursion of time window of sc administration after each daily PE to > 30 min post PE	Also dosing pre-PE is considered as major violation	██████████	Review of listings or edit	Excursion of dosing time	Treatment non compliance

Major PD categories	Remarks	Source	How to assess?	DVTERM	DVDECOD
			checks	window in daily PE period	
If $\geq 1$ dose(s) are missed during daily PE treatment period		██████████	Review of listings or edit checks	Missing dose during x days in daily PE period	Treatment non compliance
During tapered PE (as applicable) and the 30 days post daily PE treatment period					
If study drug was administered on $< 75\%$ of treatment days	If $\geq 25\%$ of doses (e.g. 0.25 x 30 days = 7.5 $\Rightarrow$ 8 days) were not administered	██████████	Review of listings or checks	Subject not dosed on x days out of y days during post daily PE period	Treatment non compliance
If $\geq 2$ consecutive doses were not administered	If PE is given (PE tapering): Drug should be given within 6 hours after PE; otherwise, consider as missing dose.	██████████	Review of listings or checks	Subject not dosed on x consecutive days during post daily PE period	Treatment non compliance
Applies to whole drug treatment period (during and after PE period)					
Randomised, no treatment administered		██████████	Review of listings or check	Randomised, no treatment	Investigator mistake
One or more incorrect (i.e. not as per randomised treatment assignment) treatment administrations		██████████	Review of CTMS entries Review of listings	Incorrect treatment administered (placebo/verum instead of verum/placebo)	Treatment non compliance
Administered more than protocol prescribed dose (overdose): if more than 1 dose and no or 1 PE on that day if more than 2 doses and not 2 PEs on that day		██████████	Review of CTMS entries	Subject overdosed (x doses instead of y)	Treatment non compliance
One PE prior to randomisation					

Major PD categories	Remarks	Source	How to assess?	DVTERM	DVDECOD
Prior to protocol amendment 12 any PE prior to randomisation is considered a major protocol deviation	Ablynx maintain a listing of which protocol version each subject is enrolled under. This will need to be used in collaboration with the PE and randomisation dates from the database in order to identify violating subjects.	██████████ ██████████	Review of listings or check	X PE done before randomisation	Eligibility criteria not met
Starting from protocol amendment 12 first PE ended more than 24h prior to randomisation is considered a major protocol deviation.	As above	██████████ ██████████	Review of listings or check	PE done x hours before randomisation	Eligibility criteria not met
Starting from protocol amendment 12 more than one PE prior to randomisation is a major protocol deviation	As above	██████████ ██████████	Review of listings or check	X PE done before randomisation	Eligibility criteria not met
Other					
Disallowed concomitant therapy taken: only one disallowed = desmopressin	Any concomitant medication with HTC code "H01BA" (coded term "VASOPRESSIN AND ANALOGUES").	██████████	Review of listings	Disallowed medication taken (name of drug, start date – stop date)	Excluded concomitant medication
Subject becomes pregnant but is not withdrawn from the trial		██████████	Review of listings	Subject pregnant but not withdrawn	Subject not withdrawn as per protocol
Subject is lost to follow up but is not withdrawn from the trial	If a subject is lost to follow up, they should be in the database as discontinued otherwise a query should fire, so at the end of the study there should be no subjects lost to follow-up who were not withdrawn.			Subject lost to follow up but not withdrawn	Subject not withdrawn as per protocol
Subject withdraws consent but is not withdrawn from the trial	If a subject withdraws consent, they should be in the database as discontinued otherwise a			Subject withdraws consent but not	Subject not withdrawn as per protocol

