7.3 Dose modification due to treatment related AE – clinically relevant bleeding

Clinically relevant bleeding is the main potential risk based on the pharmacological action of ALX-0081. It is defined as moderate to severe (including life-threatening) bleeding requiring urgent medical and/or surgical intervention. In case of clinically relevant bleeding, appropriate treatment for bleeding according to standard practice should be initiated and treatment with study drug must be interrupted. In addition, plasma levels of vWF:Ag and FVIII chromogene should be determined. If FVIII < 10%, assess for anti-FVIII antibodies and if presence is confirmed, permanently discontinue study drug. If either or both vWF and FVIII are at clinically significant low levels, administration of vWF and FVIII through commercially available combination preparations, such as Haemate-P or equivalent antihemophilic factor/vWF complex should be initiated and continued until the bleeding stops. Study drug should only be restarted when the bleeding has stopped and vWF > 50% and FVIII level is within normal range. The PE treatment, if applicable, should continue as clinically indicated.

Dosage, method of administration and duration of treatment are summarised in Table 8.

Table 8: Dosage, method of administration and treatment duration.

First study drug administration is 10 mg as an i.v. bolus, administered by a push injection, 15 minutes to 6 hours prior to initiation of PE on study.* This first PE on study is followed by subcutaneous (s.c.) administration of 10 mg study drug.

* As discussed in section 4.2, one PE session prior to randomisation is allowed. In such case, the second PE session will be the first PE on study.

S.c. study drug administration during treatment phase with PE	
Frequency of PE	Treatment administration - daily
1 PE/day	Administer 10 mg study drug within 30 min after end of PE
2 PEs/day	
 For subjects receiving anti-vWF Nanobody: administer 10 mg study drug within 30 min after each PE For subjects receiving placebo, maintain a once daily dosing regimen
Tapering (< 1 PE/day)	Daily administration of 10 mg study drug. On days with PE: within 30 min after end of PE; on days without PE at 24 h (\pm 1 h) after previous administration

S.c. study drug administration (in hospital and at home) for **30 days after the very last PE** (including tapering and PE given for exacerbations)*: 10 mg study drug once daily.

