**5. SAFETY PARAMETERS****Laboratory parameters:**

- Haematology
  - Full blood count, including red blood cells (RBC), haemoglobin, haematocrit, mean corpuscular volume (MCV), mean corpuscular haemoglobin (MCH), mean corpuscular haemoglobin concentration (MCHC), white blood cells (WBC) and differential blood count
  - Reticulocytes

- 
- Optical platelet count (if not available, can be replaced by measurement based upon impedance)
  - Immature platelet fraction (can be omitted)
  - Blood chemistry
    - Glucose
    - Haptoglobin
    - Gamma-glutamyl transferase (GGT) (screening only)
    - Bilirubin (total) (screening and baseline only)
    - Alkaline phosphatase (AP) (screening and baseline only)
    - Aspartate transaminase (AST)
    - Alanine transaminase (ALT)
    - Lactate dehydrogenase (LDH)
    - C-reactive protein (CRP)
    - Human chorionic gonadotropin (hCG) (for women, only if urine pregnancy test is not feasible or inconclusive) (baseline only)
    - Rheumatoid factor (baseline only)
    - Antinucleic acid (baseline only)
    - Iron, ferritin, transferrin (baseline only)
    - Creatinine, blood urea nitrogen (BUN), uric acid
    - Protein, albumin
    - Sodium (Na), Potassium (K), Calcium (Ca), Magnesium (Mg), Chloride (Cl)
  - Urinalysis
    - pH
    - Specific gravity
    - Protein
    - Glucose
    - Ketones
    - Bilirubin
    - Blood
    - Nitrite
    - Urobilinogen
    - Leukocytes

- 
- Urine pregnancy test for female subjects (hCG only)
  - Virus serology
    - Human immunodeficiency virus type 1 and type 2 (HIV1 and HIV2) antibodies at screening
    - Surface antigen of hepatitis B virus (HBV HbsAg) and hepatitis C virus (HCV) antibodies at screening
  - Coagulation variables (local lab)
    - Activated partial thromboplastin time (aPTT)
    - Prothrombin time (PT)
    - International normalized ratio (INR)
    - Fibrinogen
    - vWF Ag
    - FVIII chromogenic or alternative method (e.g. one stage clot test) if not available in the local lab
    - Lupus anticoagulant
    - Anticardiolipin antibodies (antiphospholipid):
      - Immunoglobulin G (IgG), Immunoglobulin M (IgM) and Immunoglobulin A (IgA)
  - Blood typing (ABO and Rhesus factor [Rh]) and direct antiglobulin test (DAT)

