### **6.2.2 Protocol Deviations**

A protocol deviation is defined as failure to fully comply with the study protocol. The deviation can be classified further as:

- 
- Minor Protocol Deviation – does not have an impact on the subject’s rights, safety or wellbeing, or the completeness, accuracy and reliability of the study data
  - Major Protocol Deviation – may affect the subject’s rights, safety or well being and/or the completeness accuracy and reliability of the study data

The sponsor will make any decisions regarding whether any subjects or any individual parameters pertaining to a subject will be excluded from the safety and efficacy evaluations when the protocol deviation is considered to have a negative impact on scientific aspects and interpretation of the study results.

Major protocol deviations will be excluded from the PP population.

All major protocol deviations will be listed. Major protocol deviations will be summarised by treatment group and overall for the ITT population.

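### SAP Appendix II counts doses withheld for bleeding, as the protocol requires, as missed doses, so compliant subjects can leave the per-protocol set; item 17 also names a bilirubin fraction absent from the listed panels

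*SAP*

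**What the plan says.** **Bleeding.** Protocol 7.3 states that on clinically relevant bleeding "treatment with study drug must be interrupted", and on resumption: "Study drug should only be restarted when the bleeding has stopped and vWF > 50% and FVIII level is within normal range". Protocol 7.6 repeats both for bleeding associated with overdose.

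SAP Appendix II has a bleeding block and then a study-drug block.

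- The bleeding block makes it a major deviation "If study drug administration is not stopped when clinically relevant bleeding occurred". One part of its database check reads "Check in DB for start date CRB = stop date study drug"; a note beside it says that the dosing date should be absent from the exposure dataset (EX).
- The study-drug block makes it a major deviation when one or more "dose(s) are missed during daily PE treatment period". During tapering and the 30 days after PE, the triggers are two or more consecutive doses not given, or dosing on fewer than 75% of treatment days. All three rows are coded as treatment non-compliance, and none mentions interruption for bleeding.

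SAP 6.2.2 says: "A protocol deviation is defined as failure to fully comply with the study protocol". SAP Section 2 fixes PP exclusions before database lock by the Appendix II criteria, without regard to assignment. It also requires PP subjects to finish the study satisfactorily.

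**Bilirubin.** Appendix II item 17 lists direct bilirubin, ALT and AST as the minimum screening or baseline liver tests, and adds: "if any of bilirubin, ALT or AST are missing or above limits in exclusion criterium, this is a major PD". SAP Section 5 lists "Bilirubin (total) (screening and baseline only"). Protocol 8.1.1, Table 10 and 8.3.1, and SAP 6.4.5, also list total bilirubin only.

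**The concern.** A correct interruption leaves a gap in the dosing record. One row of Appendix II reads that gap as compliance and the next reads it as a violation. Someone programming the missed-dose rows as written would remove subjects from PP because the site followed protocol 7.3.

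PP is the secondary efficacy population. It is used for the primary endpoint (SAP 6.3.1), for the first sensitivity analysis, and for the secondary endpoints (SAP 6.3.2). Both documents name bleeding as the main potential risk of ALX-0081, so exclusions that follow bleeding occur after randomisation and probably more often on active drug. They may also be linked to outcome. Daily PE stops largely on platelet recovery (protocol 4.3 and 7.1), so slower responders spend longer under the strict one-missed-dose rule.

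Item 17 is a separate wording conflict in the same appendix. It makes PP membership depend on a laboratory fraction that the listed panels do not contain.

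**Working it through.** The main check compares rules; the only arithmetic is an illustration of size.

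**Step 1. Run each bleeding course through Appendix II as written.**

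1. Bleed during daily PE, drug not stopped: major deviation under the bleeding row.
2. Bleed during daily PE, drug stopped, at least one dose withheld: major deviation under the missed-dose row.
3. Bleed during daily PE, drug stopped, restart conditions met before the next dose is due: no dose missed, so the missed-dose row is not triggered.
4. Bleed during tapering or post-PE dosing, one dose withheld: not a major deviation. One of 30 doses is 3.3%, below 25%, and there is no second consecutive dose.
5. Bleed in that later period, two or more consecutive doses withheld: major deviation. If 8 or more of 30 doses are withheld, the 75% row is met as well (0.25 x 30 = 7.5, rounded up to 8 in the SAP's own example).
6. Permanent discontinuation with two or more doses outstanding: major deviation, and perhaps also a failure of the completion requirement in SAP Section 2.

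Courses 2 and 5 follow protocol 7.3 and still lead out of PP. Courses 3 and 4 do not trigger the missed-dose rows. The stop that protocol 7.2 requires when a relapse occurs during post-PE dosing meets the consecutive-dose row in the same way as course 6.

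**Step 2. Compare the two halves of the bleeding check.** Take the stop date to be the date of the last dose; the SAP does not define it.

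- Bleed starts after that day's dose and dosing stops at once: the dates are equal, so the equality is met. A dose is recorded on the bleed date, so the EX note is not met for that date.
- Bleed starts before that day's dose, which is withheld: the EX note is met. The last dose was the day before, so the equality is not met.

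On that reading the two halves pass opposite cases.

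**Step 3. Item 17.** A subject with only the listed panel has a total value and no direct value. If the trigger's word bilirubin means the direct fraction named in the row, that subject is a major deviator. If it means any bilirubin result, the subject is not. A site that also recorded a direct value has no problem on this ground.

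**Step 4. Size.** The plan's 110 reproduces by the Schoenfeld formula with hazard ratio 6/3.36 = 1.786, one-sided 2.5% and 80% power: events = 4 x (1.960 + 0.842)^2 / (ln 1.786)^2 = 93.4, and 93.4 / 0.85 = 109.9. With 93.5 events (85% of 110), power is 80.0%.

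The documents give no bleeding rate for this trial, so the rates below are assumptions. They also treat every bleed as costing enough doses to trigger a row, which makes the counts upper limits for each rate.

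- ALX-0081, 5% to 15% of 55: 2.8 to 8.3 subjects.
- Placebo, 0% to 5% of 55: 0 to 2.8 subjects.

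Power of the PP log-rank test at the design hazard ratio, taking events as 85% of those remaining:

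| Assumed bleeding, ALX-0081 / placebo | Subjects lost | Power |
|---|---|---|
| 5% / 5% | 5.5 | 78.0% |
| 10% / 5% | 8.3 | 76.9% |
| 15% / 5% | 11.0 | 75.7% |
| 20% / 5% | 13.8 | 74.3% |

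The power loss is modest. Selection by arm matters more, and these figures do not measure it.

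**The case against.** The best defence is that SAP 6.2.2 already governs. A deviation is a failure to comply, the missed-dose rows are coded as non-compliance, and the bleeding row itself expects an interrupted dose, so a mandated interruption is no deviation. The sponsor also decides exclusions. This reading is available, but Section 2 sends PP membership to the Appendix II criteria, which are assessed by listings or edit checks. Appendix II writes relief where it wants it (a late negative pregnancy test, or missing AP or GGT, is minor) and writes none here. Investigators know the treatment (protocol 7.5), so a written rule is safer than case-by-case discretion.

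A second defence is that requiring adequate exposure, whatever the reason for a shortfall, is a legitimate PP choice. That is fair, but the SAP does not say it made that choice.

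Three stronger readings are tempting and are not supported.

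- A reader might infer that a bleed during daily PE removes the subject whatever the site does. An interruption may cost no dose, and after daily PE one withheld dose is tolerated.
- A reader might infer from item 17 that all 110 subjects fail and PP is empty. The trigger says only bilirubin, exclusion 17 asks sites to separate an indirect rise, and the CRF is not in the documents. The panel lists are not exhaustive either: GGT is in exclusion 17 and SAP Section 5 but not in the protocol's panels.
- A reader might infer that the date equality flags a bleed starting after that day's dose. The equality is met in that case; only the EX note would flag it.

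**Conclusion.** The point holds as a wording defect in the definition of PP and should be corrected before database lock. As written, Appendix II removes subjects managed per protocol whenever a dose is withheld in daily PE, or two or more consecutive doses are withheld later. That conflicts with SAP 6.2.2. The greater effect on the active arm is probable, since bleeding is the drug's main expected risk, but the documents do not quantify it.

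The number of subjects is unknown. The range of about 3-8 active and 0-3 placebo rests wholly on assumed bleeding rates and on each bleed costing enough doses. ITT is the primary population, so the primary test is unaffected.

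Item 17 conflicts with the listed panels unless sites also recorded a direct value; how many subjects it touches cannot be determined from the documents. Some permanently discontinued subjects may leave PP under the separate completion requirement in any case.

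**What to change.** Amend Appendix II before database lock:

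- **(a) Missed-dose rows.** State that doses withheld or stopped because the protocol requires it (7.3, 7.6, and the relapse stop in 7.2) do not count in the missed-dose, consecutive-dose or under-75% rows. State whether permanently discontinued subjects still meet the completion requirement in SAP Section 2.
- **(b) Bleeding check.** Replace the two halves with one test: flag a dose recorded after the bleed's start date and time and before the protocol's restart criteria were met.
- **(c) Item 17.** Name the bilirubin fraction actually collected. Where that is total bilirubin and it exceeds 3 x ULN, apply the criterion's haemolysis exemption through documented review made without regard to treatment assignment.

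The cost is appendix wording and edit checks, plus the review in (c), because the documents show no field that records an isolated indirect rise. A small downside is that PP keeps some subjects with shorter exposure. The changes concern analysis sets only and take no view on the clinical rules for interruption or restart.

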* As discussed in section 7.2, in case of exacerbation of TTP, standard treatment (PE) should be re-initiated and daily administration of study drug continued. The "study drug post-PE" period (for 30 days after the very last PE) will recommence once PE is again stopped. Maximum treatment duration with study drug will be limited to 90 days after first administration of study drug.

If clinically relevant bleeding* occurs

- Stop study drug administration and continue PE if clinically indicated and applicable
- Assess vWF:Ag and Factor VIII (FVIII) levels**. If FVIII < 10%, assess for anti-FVIII antibodies and if presence is confirmed, permanently discontinue study drug.
- If vWF:Ag and/or FVIII levels are at a clinically significant low level, initiate i.v. Haemate-P 50 U/kg (or equivalent antihemophilic factor/vWF complex)
- i.v. Haemate-P treatment should be discontinued when bleeding has clearly stopped and when vWF > 50%
- Restart study medication at 10 mg daily when bleeding has clearly stopped and when vWF > 50% and FVIII levels are within normal range

* Clinically relevant bleeding is defined as moderate to severe (including life-threatening) bleeding requiring urgent medical and/or surgical intervention.

** FVIII chromogene or other measure of FVIII activity

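### The SAP Appendix II row on restarting study drug after a bleed contradicts itself, and no cell tests the protocol 7.3 condition that bleeding has stopped

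*SAP*

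**What the plan says.** Protocol 7.3 gives the rule for resuming study drug after an interruption for clinically relevant bleeding: "Study drug should only be restarted when the bleeding has stopped and vWF > 50% and FVIII level is within normal range". Table 8 repeats it: "Restart study medication at 10 mg daily when bleeding has clearly stopped and when vWF > 50% and FVIII levels are within normal range". Table 1 and section 7.6 (overdose) carry the same three conditions.

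SAP Appendix II has a row for breaches of this rule. Three of its cells matter:

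- Category (first column): "If study drug is restarted when vWF:Ag < 50% and FVIII not normalised"
- Remarks, after a CRF monitoring check: "Check in DB for start date of study drug ≥ date of local lab vWF:Ag > 50% and FVIII value in normal range"
- DVTERM: "Drug restarted but vWF:Ag and FVIII levels not recovered yet"

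The row above it deals with the onset of the bleed: "If study drug administration is not stopped when clinically relevant bleeding occurred". Its database check is "start date CRB = stop date study drug", supported by the action-taken field of the adverse event.

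SAP section 2 uses the Appendix II criteria to decide who leaves the PP population. SAP 6.2.2 lists major deviations and summarises them by treatment group and overall in the ITT population.

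**The concern.** A rule that needs three conditions to hold together is broken when any one of them fails. The category text joins two failures with a conjunction, so it describes only restarts in which both levels are unrecovered. The Remarks check joins two recoveries, so it describes restarts in which at least one level is unrecovered. The two cells can therefore classify the same subject differently, and the DVTERM can be read either way.

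The third condition, that bleeding has stopped, appears in no cell of the row. The row above does not supply it, because it looks only at whether dosing stopped when the bleed began.

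Protocol 7.3 calls clinically relevant bleeding the main potential risk of ALX-0081, so the reported count of breaches of this rule should be reproducible and complete. As written, two programmers could derive different counts from the same row, and neither count would cover the whole protocol rule.

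**Working it through.** The plan gives no figure to reproduce, so the check is to set the rules side by side and enumerate the possible states at restart.

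**Inputs.** B = bleeding stopped, V = vWF:Ag above 50%, F = FVIII in normal range (protocol 7.3, Table 8). The category text and Remarks check come from SAP Appendix II. I assume that the Remarks check refers to levels drawn after the interruption.

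**Rules.**

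- Protocol breach: not (B and V and F), that is, not B or not V or not F.
- Category text flags: vWF:Ag below 50% and not F.
- Remarks check flags: not (V and F), that is, not V or not F.

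**Two levels of vWF:Ag** (2 × 2 × 2 = 8 states):

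| Bleeding stopped | vWF:Ag > 50% | FVIII normal | Protocol 7.3 | Category text | Remarks check |
|---|---|---|---|---|---|
| yes | yes | yes | permitted | no flag | no flag |
| yes | yes | no | breach | no flag | flag |
| yes | no | yes | breach | no flag | flag |
| yes | no | no | breach | flag | flag |
| no | yes | yes | breach | **no flag** | **no flag** |
| no | yes | no | breach | no flag | flag |
| no | no | yes | breach | no flag | flag |
| no | no | no | breach | flag | flag |

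One state is permitted and 7 are breaches. The category text flags 2 of 7 and the Remarks check 6 of 7. The one state that both miss is a restart with both levels recovered while bleeding continues.

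**vWF:Ag of exactly 50% as a third level** (2 × 3 × 2 = 12 states, 11 breaches). The protocol requires more than 50%, whereas the category text begins below 50%. The category text flags 2 of 11. The Remarks check flags 10 of 11 and misses the same single state.

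**Is the missed state plausible?** Protocol 7.3 provides for a vWF/FVIII concentrate when levels are low, and Table 8 makes ending it depend on bleeding status and vWF level separately. The protocol itself thus treats levels and bleeding as distinct, and levels could recover before the bleed ends.

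**Effect on PP membership.** A restart follows an interruption, and Appendix II also counts missed doses as major deviations. During daily PE, one missed dose is enough. Afterwards it takes two consecutive missed doses, or dosing on fewer than 75% of days. A single missed dose in a 30-day post-PE period (1/30 = 3.3%, against the 25% limit) triggers neither of the later rules. In that case the restart row alone can decide whether the subject stays in PP.

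These are counts of logical states, not expected numbers of subjects.

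**The case against.** The strongest reply is that the Remarks cell is the operational test and the category text only a label. On that view a restart with just one level unrecovered is caught. This stands in part: a reader might infer that such restarts go uncounted, but that follows only if the category text is what gets programmed. It does not answer the contradiction between the cells or the missing bleeding condition.

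Other stronger readings are also tempting, and the documents do not support them:

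- **That this row is the SAP's only check on the bleeding rule.** The row above tests interruption at onset, both rows call for CRF monitoring, SAP 6.4.1 and 6.4.6 tabulate interruptions and bleeding, and SAP section 2 mentions a separate tracker of clinical deviations.
- **That subjects restarted in breach generally stay in PP.** Most would already leave through the missed-dose rows. Those rows code the event as treatment non-compliance, however, so the restart breach itself is not identified.
- **That the under-count falls mainly on ALX-0081.** Investigators know the assignment (protocol 7.5) and bleeding is the drug's expected risk, but no rate of bleeding followed by restart is given for either arm.
- **That protocol Table 6 sizes the problem.** Summing the differences between the numbers below 50% for vWF and FVIII gives at least 3+0+0+2+0+2+0 = 7 of 27 discordant ALX-0081 subjects (26%), or 0+2+0 = 2 of 15 in the 10 mg groups. These are healthy volunteers on drug, not patients at restart, and 50% merely stands in for an FVIII normal range that the documents do not give. The table shows that the two levels can diverge and nothing more.

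A fair point about the remedy is that an adverse event may stay open after active bleeding has ended, so a bare comparison with its stop date could flag permitted restarts. The fix has to allow for that.

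**Conclusion.** The row is wrong as written, at low severity. Its category text and Remarks check disagree, and under either one a restart during continuing bleeding with recovered levels is not flagged. The consequence is possible misclassification in the major-deviation listing and by-arm summary. PP membership is affected mainly for subjects not already removed by the missed-dose rows, such as one with a single missed dose after daily PE.

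The ITT primary log-rank analysis does not use this row and is unaffected. Only subjects with a clinically relevant bleed followed by a restart are concerned, and the documents give no basis for estimating how many there will be. The conclusion rests on reading the conjunction in the category text literally and on the assumption about the Remarks check stated above.

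**What to change.** Before database lock, reconcile the category text, Remarks check and DVTERM with protocol 7.3, so that the deviation is a restart with any one of the protocol's stated conditions unmet. This includes covering vWF:Ag of exactly 50%. Add a comparison of the restart date with the recorded end of bleeding, taken from the bleeding assessments or the adverse event stop date, and review by hand any case where the event stayed open after active bleeding had ended. A row written this way flags 7 of 7 breach states (11 of 11 with the 50% level separated) and leaves the permitted state unflagged.

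The cost is one amended SAP row, one added date check and some manual review before lock. The change aligns the SAP with the protocol's own text and leaves the clinical rule as it is.
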